1 STATEMENT OF COMPLIANCE

The Implementation of Decision Aid for Lupus Patients in Practice Settings for Shared Decision-Making (SDM): IDEAL Study will be conducted in accordance with the International Conference on Harmonization Good Clinical Practice (ICH GCP), applicable United States (US) Code of Federal Regulations (CFR), and Patient Centered Research Outcomes Institute (PCORI) Terms and Conditions of Award. The Principal Investigator ([name], MPH) will ensure that no deviation from, or changes to the protocol will take place without prior agreement from the PCORI, and documented approval from the Institutional Review Board (IRB), except where necessary to eliminate an immediate hazard(s) to the trial participants. All personnel involved in the conduct of this study have completed Human Subjects Protection and ICH GCP Training.

The protocol, informed consent form(s), recruitment materials, and all participant materials have been submitted and approved by the University of Alabama at Birmingham (UAB) Institutional Review Board (IRB). Any amendment to the currently approved protocol will require review and approval by the IRB before the changes are implemented to the study. All changes to the consent form will be IRB approved; to be obtained from any participants who provided consent, using a previously approved consent form.

2 PROTOCOL SUMMARY

2.1 Synopsis

Title:	Implementation of Decision-Aid for Lupus Patients in Practice Settings for Shared Decision-Making (SDM): IDEAL study.
Study Description:	We are proposing to put into practice a shared decision-making (SDM) strategy (a decision making process jointly shared by patients and their health care providers) using an individualized, computerized decision aid (DA; a tool to help each person make individual treatment decisions) for Systemic lupus erythematosus (SLE), also commonly called lupus, which is culturally appropriate for lupus patients.
Objectives:	Specific Aim 1: Conduct a formative evaluation in 16 diverse clinics to assess stakeholder needs and identify clinic and contextual characteristics (e.g., readiness for change, physician attitudes, patient barriers) to inform strategy component selection and influence implementation effectiveness of lupus DA (Aim 2). Specific Aim 2: Assess the effectiveness of a multi-component (standardized and tailored) strategy for the implementation of the DA in 16 lupus clinics (minimum 35 patients/clinic) by examining changes in subjective and objective measures of implementation effectiveness over 27-months. Specific Aim 3: Identify opportunities for sustaining and disseminating the DA via semi-structured debriefing interviews with key clinic informants of Aims 1 and 2 and patients and develop a manual that provides step-by-step implementation guide for incorporating the DA into regular lupus clinic visits and care pathways.
Study Population:	Male/Female Lupus Patients Key Clinic Personnel
Description of	Participants will be recruited from n=16 sites, listed below:

Sites/Facilities Enrolling Participants:	
1. Baptist Health,2. Ohio State University3. Loyola University,4. Vanderbilt University,5. University of California Los Angeles,6. Medical University South Carolina,7. Baylor University,8. Emory University,9. Northwestern University,10. Northwell Health,11. University of Mississippi,12. University of California San Diego,13. University of Alabama, Birmingham (UAB)14. Cedars-Sinai Hospital,15. University of Chicago,16. University of Illinois at Chicago
Study Duration:	27 months
Participant Duration:	6 Months

2.2 Table 1. Schedule of Activities (SOA)

IDEAL Study Timeline and Milestones

Activity (by Quarter(Q) of Study)	Q 1	Q 2	Q 3	Q 4	Q 5	Q 6	Q 7	Q 8	Q 9	Q 10	Q 11	Q 12
Study Management and Recruitment												
Finalize study consent, recruiting materials, and train staff	X											
Submit for IRB Approval at UAB + 15 sites	X											
Network Meta-Analysis for Decision-Aid and updating content	X											
Participant enrollment												
Aim 1: Semi-Structured Interviews & surveys; Clinic Staff	X	X										
Aim 2: Patient Enrollment												
Begin study enrollment		X										
Enrollment 25% complete				X								
Enrollment 50% complete						X						
Complete study enrollment										X		
Clinic Personnel Exit Interview**												
Aim 2: Clinic Personnel surveys		X		X				X				
Aim 3: Semi-Structured Interviews; Patients + Clinic Staff										X		
Study Coordinator 6 month Survey		X		X		X		X		X		X
Draft abstracts/manuscripts for presentation publication											X	
Submit abstract/manuscripts for presentation/publication												X
Data Management and Analysis												
Finalize study questionnaires and analysis plan	X											
Begin data analysis										X		
Complete Data Analysis and Implementation manual												X
Complete data analysis of study endpoints												X
Reports to Funding Agency (PCORI)												
D&I evaluation Plan Template completed	X											
Complete Interim Progress Report		X				X			X			
Complete update on evaluation work				X								
Evaluation of sustainability and next steps												X
Final Progress Report												X

**Only conducted if clinic personnel transitions to another position or leaves the organization.

Aim 1 clinic personnel semi-structured Interviews & surveys focused on understanding organization's ability to change, the clinic structure and function, clinic flow and the clinic's team interaction will be done once at the baseline.

Aim 2 clinic personnel surveys will be done at 0, 6, 12, and 24 months to assess the acceptability, appropriateness, feasibility, success, permanence of the DA. Baseline surveys will be completed in the Q1-Q2. Health care utilization by patients (inpatient and urgent care) and DA penetration will be assessed using administrative data.

Aim 2 patient assessments with surveys will be done on the day of clinic visit (0-month in-person), and then at 3- and 6-months, to be done via phone, mail, or at the regularly scheduled clinic visit per the patient participant preference.

Surveys will assess patient satisfaction with DA, its acceptability and feasibility, patient perception of DA usefulness (PDM), decision conflict, decision involvement, care process/communication (IPC, audiotaped conversation), DA review time.

Aim 3 clinic personnel semi-structured Interviews will be done once with same people as in aim 1 to assess the level of DA integration into clinics and the implementation lessons learnt.

Aim 3 patient semi-structured Interviews will be done once with 2 patients/clinic.

3 INTRODUCTION

3.1 Study Rationale

In a PCORI funded and recently completed multicenter randomized trial, 301 high-risk adult women with lupus kidney disease, including racial/ethnic minorities with low socio-economic status, either received the lupus DA (decision-aid) or the American College of Rheumatology (ACR) lupus paper pamphlet with information on treatments. Compared to the ACR paper pamphlet, people who used the lupus DA had a much greater decrease in decisional conflict (uncertainty in choosing options) for immunosuppressive drugs and were much more likely to choose the treatment option most consistent with their values, having viewed information that mattered the most for the treatment decision. Compared to the pamphlet group, more patients rated the information in lupus DA to be excellent for understanding the impact of lupus (49% vs. 33%), risk factors (43% vs. 27%), medication options (50% vs. 33%), evidence about medications (47% vs. 24%); and rated the ease of use of materials higher (51% vs. 38%). This study will put into practice a shared decision-making (SDM) strategy, using the individualized, culturally sensitive, computerized decision-aid for systematic lupus erythematosus (SLE) patients.

3.2 Background

Lupus is a rare disease with significant health impact, disparities and decision-making challenges - Lupus is a rare autoimmune disease of young women with significant health outcome disparities (PCORI priorities), with 2.4-times higher mortality than age-matched controls. It affects 0.1% of the population, but lupus nephritis (kidney disease) accounts for 2% of all end-stage renal disease in the U.S. Decision-quality in lupus is poor; many patients decline lifesaving immunosuppressive medications, due in part to the lack of recognition of benefits and a fear of harms. Long-term immunosuppressive drug and glucocorticoid (called “steroid”, “Medrol” or “prednisone”) therapy, often lifesaving and kidney-saving, can be complex and has significant risks including serious infections, shingles and infertility, significantly affecting young women of child bearing potential.

3.3 Risk/Benefit Assessment

3.3.1 Known Potential Risks

Beyond potential anxiety from responding to questions and considering treatment options, there are no anticipated risks to participating in Specific Aim 2 (patient review of decision-aid, feasibility and acceptability assessments) and Specific Aim 3 (semi-structured quantitative interviews with selected patients). Although it is possible that clarification of treatment options will increase the indecision in some patients, previous studies of decision-aids show that more information leads to a decrease in decisional conflict. Similarly, the clinic staff providing their opinions as part of Aims 1-3 could have potential anxiety from responding to questions.

3.3.2 Known Potential Benefits

Participants will not directly benefit from participation in this study; however, it is our hope that patients will be better informed about their treatment options.

The major benefit of this research is for lupus patients in the future. If we can implement this decision-aid tool in regular clinics and integrate it with the patient clinic flow, patients with lupus will have access to it in the future. The lupus decision-aid tool may help with patient decision making and informed choice and patients may be more satisfied with their decision-making. This non-proprietary tool in the public domain will be available to all lupus patients for use in decision-making regarding immunosuppressive drugs.

3.3.3 Assessment of Potential Risks and Benefits

A potential benefit from this study is that the knowledge gained will provide patients valuable information about lupus and its treatment, as well as to inform clinicians about the best way to implement the decision-aid into normal clinic workflow.

We will take the following precautions to avoid/minimize risks to participants:

Patient participant initial data and responses to questionnaires will be captured during regularly scheduled lupus clinic visits. Follow-up surveys will be conducted via phone, email, or in the clinic visit depending on the preference of the patient. All clinic personnel surveys and interviews will be conducted during general work hours (even before or after their shift). All semi-structured in-depth interviews will be captured via phone and transcribed for accuracy as soon as possible. All data (except data from semi-structured interviews) will be entered into coded electronic case report forms (CRF) and will be checked by study personnel daily for accuracy. On a quarterly basis study investigators and research team will review GCP, human subject's protections/confidentiality, and study procedures. The research team will meet biweekly to review recruitment, enrollment, source documents, and electronic case report forms; in the event an adverse event occurs this will be reported to the UAB IRB at the time of continuing review. All serious adverse events (SAEs) will be reported to the IRB and PCORI within 48 hours of the Principal Investigator becoming aware of the event. All research team members will be informed by the PIs about any unanticipated problems involving risks to the participant. If any protocol changes are needed, the PIs will submit a modification request to the IRB. Protocol changes will not be implemented prior to IRB approval unless necessary to eliminate apparent immediate hazards to the research participant. In such cases, the IRB will be promptly informed of the change following implementation (within 1 week).

Considering the aim of this study is to determine best practices for implementation of a treatment decision aid it poses no more than minimal risk to participants. We will use a secured database to minimize the risk of disclosure of personal health identifiers (PHI) therefore no Data Safety Monitoring Board (DSMB) will be convened.

4 OBJECTIVES AND ENDPOINTS

Specific Aim 1: Conduct a formative evaluation and introduction to the DA in 16 diverse clinics to assess stakeholder needs and identify clinic and contextual characteristics (e.g., readiness for change, physician attitudes, patient barriers) to inform strategy component selection and influence implementation effectiveness of lupus DA (**Aim 2**). Penetration will be assessed by evaluating the proportion of eligible patients reviewing the DA overall and in each site. Patient healthcare utilization outcomes (e.g., inpatient visits and ER/urgent care visits) will be assessed similarly.

Specific Aim 2: Assess the effectiveness of a multi-component (standardized and tailored) strategy for the implementation of the DA in 16 lupus clinics (minimum 35 patients/clinic) by examining changes in subjective and objective measures of implementation effectiveness over 27 months. Objective measures will be assessed in both clinic personnel and in patients. Clinical personnel will evaluate perceived acceptability of intervention measure for the DA, perceived DA implementation success, and perceived DA permanence. All will be assessed on a Likert-type scale. Similarly, patients will evaluate perception of DA usefulness, patient satisfaction for the DA, perceived intervention appropriateness measure for the DA, and perceived feasibility of intervention measure for the DA. All of these patient assessments will be measured on a Likert-type scale.

Specific Aim 3: Identify opportunities for sustaining and disseminating the DA via semi-structured debriefing interviews with key clinic informants of Aims #1 and patients of Aim 2 and develop a manual that provides step-by-step implementation guide for incorporating the DA into regular lupus clinic visits and care pathways.

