The baseline visit will take approximately 1 hour to complete. All patients with lupus are eligible. The study coordinator will approach patients at their regularly scheduled lupus clinic appointments. Once the potential participant checks in either at a kiosk or with a front desk clerk, they will be made aware of the lupus decision-aid by either the clinic clerk or the study coordinator. The study coordinator will then approach the patient participant and invite them to participate in the study. If a patient participant declines the invitation to participate, the reason will be recorded in the excel spreadsheet. If the patient participant agrees to participate, he/she will be given a non-signature consent form which

explains the study objectives. The patient participant will be given the necessary time to read the non-signature consent form and ask any questions they have to the study coordinator. No signature will be necessary on the consent form. Participants will be required to sign a paper HIPPA form since study coordinators will view limited personal health identifiers (PHI) (medical record number, voice from conversations with physicians). The coordinator and patient participant will be required to sign the HIPPA form, and a copy will be given to the patient participant, as well as being placed in their file.

After the non-signature consent form is given to the patient participant, study procedures will begin and a participant number will be assigned. During the baseline visit, the following procedures will be performed and information will be obtained to determine eligibility to continue in this research study:

- Review inclusion/exclusion criteria
- Date of birth
- Self-reported race/ethnicity

Patient participants will be invited to watch a short informational video on the iPad and review the DA, before beginning the assessments. After completing the questionnaire, patients will complete a W-9 form that allows payment to be processed. Participants will be compensated via a paper check from the Data coordinating center that will take up to 7 business days to be issued, per institutional accounts payable procedures. Patient participants will receive payment (\$50) after the initial visit has been completed.

Each patient participant will be reminded of the three and six month follow-up phone calls prior to the visit departure.

Specific Aim 2: Follow-up Patient Participants

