We will follow each patient participant from screening for up to six months until completion of the full study (week 26). Unless the subject withdraws consent, the subject will be followed for the full study period and all data will be collected as scheduled. At three and six months post baseline visit, patient participants will be administered a 15 minute survey. Patient participants will receive a \$10 payment (via check) from Data Coordinating Center after each survey has been completed. Non-responders will be administered the survey on their next regularly scheduled lupus clinic visit.

Specific Aim 2: Clinic Personnel Survey

Up to 15 clinic personnel, the same clinic personnel as surveyed in Aim 1, will be administered an online survey via Qualtrics® at 0-, 6-, 12- and 24-months to assess their perception of appropriateness, acceptability, success, permanence and feasibility of the decision-aid. This will last between 20-25 minutes. Clinic personnel will be emailed a link to complete the survey. An automatic email will be generated in the Qualtrics® system and will go out to all non-responders every 24 hours for 5 days, or until the survey is completed.

Specific Aim 3: Semi-Structured Interviews

Clinic personnel interviewed for Specific Aim 1, as well as 2 participants at each site (selected by the site PI), will be administered a 45-60 minute, semi-structured phone interview. This interview will identify opportunities for sustaining and disseminating a lupus DA and help to develop a manual that provides a step-by-step implementation guide for incorporating lupus DA into regular clinical visits and care pathways for patients with lupus. This Specific Aim will result in: 1) knowledge of key lessons learned about the implementation process; 2) challenges to sustaining use of the DA; and 3) a manual that provides step-by-step implementation guide for incorporating lupus DA into regular clinical visits and care pathways for patients with lupus. Questionnaires will be adapted as in Specific Aim 1 to fit each time range, key personnel, and to account for any turnover in personnel interviewed in Specific Aim 1.

Study Coordinators

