For individual-level outcomes, initial analyses will focus on how clinic personnel and patient perceptions change over time. We will examine mean levels (total change) and patterns of change (growth trajectories) while controlling for differences between clinics using multivariable models that account for repeated measures and clinic clustering of patients (i.e., generalized estimating equations (GEE) with robust standard errors). The second component of our evaluation of **Aim 2** will use fuzzy set Qualitative Comparative Analysis (fsQCA) to assess the effectiveness of implementation strategies for clinic-level outcomes. fsQCA is a case-oriented approach that examines relationships between conditions (similar to explanatory variables in regression models) and outcomes using set theory to answer the question: “what conditions, alone or in combination, are necessary or sufficient to produce an outcome?”

For patient-physician communication analysis, question-asking, assertive responses, and expressions of concern will be coded as patient participation; supportive talk and partnership building by provider will be coded as active physician communication.

Specific Aim 3:

Similar to **Aim 1**, emergent theme analysis within each clinic will be initially conducted. These themes will focus identify the implementation lessons learned by the clinics, including and especially the implementation challenges faced by the clinic throughout the study, and their opinions of the opportunities and challenges to sustaining use of the DA once the study ends. These within-case themes also will be used to compare and contrast between clinics to identify common lessons learned and ideas for how to sustain the DA moving forward.

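### The Aim 2 patient model has no term for when in the implementation period a patient enrolled, so it does not estimate patient-rated change over 27 months

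*Combined protocol and SAP*

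**What the plan says.** Section 4 sets Aim 2 as assessing the strategy "by examining changes in subjective and objective measures of implementation effectiveness over 27 months". The measures listed there include patient-rated usefulness, satisfaction, appropriateness and feasibility as well as staff ratings.

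The notes to Table 1 (Section 2.2) give the patient timing: "Aim 2 patient assessments with surveys will be done on the day of clinic visit (0-month in-person), and then at 3- and 6-months". Section 8 (Patient Baseline Visit) places the first survey after exposure to the DA: "Patient participants will be invited to watch a short informational video on the iPad and review the DA, before beginning the assessments". Follow-up ends at six months.

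For individual-level outcomes, Section 9.4.2 says that "initial analyses will focus on how clinic personnel and patient perceptions change over time", using GEE models that allow for repeated measures and clinic clustering. Section 9.1 adds a strategy-group covariate to test whether trajectories differ. Neither section says from what point time is counted. Neither names enrolment date, calendar time or months since the clinic started.

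Table 1 puts "Begin study enrollment" in Q2 and "Complete study enrollment" in Q10. Staff are surveyed at 0, 6, 12 and 24 months of the study, and coordinators are interviewed every six months (Sections 6.1 and 8).

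**The concern.** The strategy acts on clinics over study time, through refresher training every six months, audit and feedback, huddles and intake reminders. If these improve how the DA is delivered, or if delivery decays, the natural place to see it in patient data is the contrast between early and late enrollees at month 0. The plan does not make that contrast. A patient who enrols in a clinic's first month and one who enrols two years later, after several refreshers and the COVID-19 changes in Section 10.5, enter the model at the same time point.

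At stake is the patient part of a stated aim. A rejected null for patients would describe change after DA review. The strategy comparison for patients would compare those post-review trajectories, which are not the course of implementation over 27 months.

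**Working it through.** **Plan's own figures.** The plan gives no power or precision for change over time. Section 9.2 gives 95% CI widths for a single proportion or mean: 5.3%, 8.1%, 0.09 and 0.35. With ICC 0.05 and 35 patients per clinic, the design effect is 1 + 34 × 0.05 = 2.7, the effective size is 560/2.7 = 207, and the widths are 8.2%, 13.3%, 0.14 and 0.54. The stated widths are therefore not reproduced. That is a separate matter, and nothing below uses them.

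**Time axes.**
- Patient time: 0, 3 and 6 months from the patient's own DA review (Sections 2.2 and 8).
- Entry period: Q2 to Q10 inclusive = 9 quarters × 3 = 27 months (Table 1).
- Entry pattern: 25% enrolled by Q4 and 50% by Q6. Uniform entry would give 3/9 = 33% and 5/9 = 56% by the end of those quarters, so uniform entry is a fair approximation.

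**What the planned slope picks up.** A simulation used 1,000 runs, 16 clinics × 35 patients, ICC 0.05 and clinic-clustered robust standard errors. Total SD 1, within-patient correlation 0.5, uniform entry and a true drift of ±0.5 points over 27 months are assumptions. There was no change due to patient time itself.
- *A: ratings reflect the clinic's state when the patient reviewed the DA.* The 0-to-6-month change was estimated at about 0.00 and was significant in 5% to 6% of runs, which is the false-positive rate. An added enrolment-date term recovered ±0.50 and was significant in about 98%.
- *B: ratings track the clinic's state on the survey date.* The expected 6-month change is 0.5 × 6/27 = 0.11. The planned slope gave 0.11 and was significant in about 69% of runs. It cannot be told apart from patients' own change after the DA. The added term again recovered ±0.50 (97% to 98%).

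**Precision of the missing analysis (month-0 scores).** With uniform entry, the SE of the change over the whole 27 months is SD × √(1 − ICC) × √12 / √N.
- N = 560: 1 × 0.975 × 3.464 / 23.66 = 0.143.
- N = 3,000: 1 × 0.975 × 3.464 / 54.77 = 0.062.
- A separate simulation (300 runs) gave 0.135 and 0.064 (at N = 3,008).
- At the SDs used in Section 9.2, 0.5 and 2.0, these become 0.07 and 0.29 at 560, and 0.03 and 0.12 at 3,000.
- Smallest change detectable with 80% power (× 2.80, SD 1): 0.40 and 0.17 points.

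Entry time varies within clinics, so the ICC does not inflate this SE if clinics share one trend.

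**Where the SE grows.**
- Strategy-by-time term, two equal groups: each slope rests on N/2, so the difference has SE 2 × 0.143 = 0.29 or 2 × 0.062 = 0.12.
- Clinic-specific trends: with an assumed between-clinic SD of 0.5 in the 27-month change, the SE at 3,000 is √(0.062² + 0.5²/16) = 0.14, and twice that, 0.28, for the interaction.
- A COVID-19 period indicator is itself a step in time. For a step after a fraction q of uniform entry, its squared correlation with entry time is 3q(1 − q). At q = 0.5 this is 0.75, so the SE is multiplied by 1/√0.25 = 2.

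**The case against.** The strongest reply is that this is a specification gap in one part of the aim. The 27 months is also the stated study duration, and the sentence in Section 4 covers staff and patient measures together. Staff surveys run to 24 months. Coordinators are interviewed every six months, and periodic check-ins (Section 6.3) gauge how far the DA has entered clinic flow. Strategy effects on clinic-level outcomes are assigned to fsQCA. All of this stands, and it confines the gap to the patient side. It does not close it: fsQCA as described relates conditions to outcomes and names no time component.

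A reader might infer that the patient analysis cannot detect implementation change at all, or would report no change whichever way delivery moved. The documents do not support that. Follow-up asks about experience at the clinic as well as the guide, and patients may re-review the DA at 3 and 6 months (Section 10.5), so case B is plausible and some drift would then enter the slope. For the same reason the patient slope should not be read as change after a single viewing.

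It is also fair to object that time since first enrolment is mixed with the COVID-19 changes (DA on the patient's phone or on paper, proposed virtual enrolment) and with patient mix. Section 6.3 expects 16 different approaches, which makes a common trend doubtful. Both points stand. They limit what the added analysis can claim, but they do not justify leaving it out.

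**Conclusion.** The point holds for patients. The planned model neither estimates early-versus-late change across the 27-month entry period nor separates it from change after DA review. The omission lies in the analysis, because staggered entry supplies the data. It is more than missing detail: followed as written, the plan leaves the patient part of a stated aim unestimated.

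The standard errors of about 0.14 (560 patients) and 0.06 (3,000) rest on SD 1, uniform entry and a common linear trend, with no COVID-19 term. The strategy interaction has about twice those values. Clinic-specific trends or a period indicator would enlarge both.

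Penetration is also planned only as an overall and per-site figure. A reader might count that as a second broken promise, but Section 4 places penetration under Aim 1 and does not promise a trend.

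**What to change.** - State in the SAP what time means in each Aim 2 model. For patients, say whether it is nominal visit or actual days, since Section 10.5 allows 61 to 150 days for the 3-month survey and 151 to 356 for the 6-month survey.
- Add a patient-level model of month-0 scores on months since the clinic's first enrolment, or since its launch date if recorded. Include clinic clustering, patient demographics and an indicator for the COVID-19 period or mode of DA delivery.
- Add a strategy-by-time term, labelled exploratory.
- Keep the 0-3-6-month model as the analysis of durability after DA review.
- Report the new model as descriptive, because implementation time stays partly confounded with COVID-19 changes and patient mix.
- Report penetration by period only where sites can supply dated counts. Section 9.3 asks them only for totals over the active study period.

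The cost is SAP wording, one derived variable and one more planned analysis. No extra patients or surveys are needed. The documents do not say that launch dates are recorded, which is why first enrolment is the default origin. Penetration by period would need additional reporting from sites.
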